**Randomized Controlled Trial of Talc Instillation In Addition To Daily Drainage
Through a Tunneled Pleural Catheter to Improve Rates of Outpatient
Pleurodesis in Patients with Malignant Pleural Effusion – The ASAP II Trial**

Participating Sites:

Duke University Medical Center

Durham VA Medical Center

NCT04792970

Version Date: 01/01/2021

Purpose of the Study

To assess the efficacy of talc instilled via tunneled pleural catheter combined with daily drainage to induce accelerated pleurodesis in patients with malignant pleural effusion. *Our hypothesis is that the combination of talc instillation with daily drainage will increase rates of pleurodesis compared with daily drainage alone.*

Background and Significance

Tunneled Pleural Catheters (TPC's) are an increasingly utilized for the management of malignant pleural effusions (MPEs). TPCs provide rapid relief of dyspnea and improvement in quality-of-life in patients with MPEs.^{1,2} Spontaneous pleurodesis may occur through repetitive drainage of the pleural space, however the rates and timing of this event are variable and have been reported to be between 16% and 65%.^{1,3,4} Earlier pleurodesis leads to lower supply costs and reduced risk of long term complications such as infection, pain or mechanical failure.^{5,6} This is especially important as malignant pleural effusion is associated with a generally poor prognosis and if given limited life expectancy, minimizing medical interference and hospitalized days is paramount.^{7,8}

Recent advances in the field of malignant pleural effusion management have prioritized these patient centered goals of maximizing quality of life improvements while minimizing time in the hospital. Recent research by our own group has shown a 20% improvement in the percentage of patients having their TPC removed by 12 weeks with high volume daily drainage of pleural effusions at home.⁹ Parallel research has demonstrated that the addition of talc through a TPC achieves a similar 20% improvement in pleurodesis within the first 5 weeks.¹⁰ Somewhat surprisingly, the rates of pleurodesis were nearly identical between the 2 studies at 48% and 43% respectively^{9,10}. Notably, patients in the talc study drained their effusions using an every other day or symptom guided strategy rather than daily drainage.

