Cost to the Subject- There will be no increased cost of care to the patients as the instillation will occur during routine follow up visit after TPC placement. Talc will be supplied as part of clinical care. Clinic visits are occurring as part of our routine clinical care for malignant pleural effusion treated with tunneled pleural catheters. Drainage bottles will be obtained through usual care pathways.

Data Analysis and Statistics

Power Calculation

Assuming a 45% rate of TPC removal in the control arm, and a 65% rate of TPC removal in the experimental arm (a 20% improvement) and a margin of error of 5% we calculate we would need to enroll 92 patients per group to have 90% power to detect a significant difference with $p<0.05$ using a one sided superiority test. Given a 10% dropout rate seen in the other two major studies within this field, we assume we would need 101 patient's per treatment arm. We anticipate including 2 centers in this study and we estimate that accrual will be reached within 36 months. Study will be completed at 40 months to allow for complete follow up of all patients enrolled.

[figure not shown]
Statistics will be performed by a statistician blinded to which treatment group allocation

Planned Interim Analysis

An interim analysis will be conducted once 100 subjects have been recruited and 90 day data collected. Analysis will be for the primary outcome only. Statistically significant difference in pleurodesis rates as measured by Fisher's Exact Test with $p < 0.05$ will trigger early termination of the study.

Data and Safety Monitoring

All study records will be kept securely by in the study coordinators or local site investigators office. Digital records will utilize secured Redcap database software on the Duke or VA networks. Only the study personnel will have access to the records. Subject data will be coded with a study number after recruitment. The code crosswalk key will be kept in a separate location from the study data.

References

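### The interim look stops the trial at an unadjusted Fisher p<0.05 with no sidedness, direction or alpha split, so the one-sided 5% level is not controlled by design

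*Combined protocol and SAP*

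**What the plan says.** The Purpose of the Study section states a directional hypothesis: "the combination of talc instillation with daily drainage will increase rates of pleurodesis compared with daily drainage alone". The Power Calculation follows that direction. It sizes the trial at 92 per group, raised to 101 for 10% dropout, "to have 90% power to detect a significant difference with $p<0.05$ using a one sided superiority test". It does not mention an interim look.

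The Planned Interim Analysis section then says: "An interim analysis will be conducted once 100 subjects have been recruited and 90 day data collected". The look is confined to the primary outcome, and the rule is mandatory: "Statistically significant difference in pleurodesis rates as measured by Fisher's Exact Test with $p < 0.05$ will trigger early termination of the study".

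Neither section says whether the Fisher test is one- or two-sided or which direction of difference counts. Neither gives the level left for the final analysis. The text names no final test. A figure after the power calculation is not shown and might name one, and nothing below relies on its absence. The Data and Safety Monitoring section deals with record keeping and adds no boundary. On who runs the tests, the plan says: "Statistics will be performed by a statistician blinded to which treatment group allocation".

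**The concern.** A design with one 0.05 test can declare talc superior once. A second chance at the interim adds false-positive error unless the final level is lowered or the interim threshold is made stricter, and the plan does neither. The amount added depends on the sidedness of the interim test, which is unstated and could still be settled after data are seen.

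The missing direction matters separately. As worded, a significant result favouring daily drainage alone would also end the trial, and the one-sided design does not address that outcome.

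This look would often decide the trial. If the planned effect is true, it ends 39-55% of such trials, so the primary conclusion would frequently rest on this rule.

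**Working it through.** **Inputs.** From the Power Calculation: 45% control and 65% talc, one-sided 0.05, 90% power, 92 per group, 101 with dropout. From the Planned Interim Analysis: 100 subjects, Fisher p<0.05.

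**Assumptions.** 50 per arm at the interim (1:1 allocation is implied by equal arms, not stated) and a final test at the full one-sided 0.05 (inferred from the power calculation). With 10% dropout at both looks the counts become 45 at the interim, then 0.9 × 92 ≈ 83 or 0.9 × 101 ≈ 91.

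**The plan's own figure.** The usual pooled formula is n = [1.645√(2 × 0.55 × 0.45) + 1.282√(0.45 × 0.55 + 0.65 × 0.35)]² / 0.20² = (1.157 + 0.884)² / 0.04 ≈ 104.1, so 105 per group. The stated 92 is not reproduced: it gives 86.5% power by this approximation, and 101 gives 89.2%. That is a separate matter, but it bears on the cost of the fix.

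**Two-look error.** For a common null rate p, talc-favouring error = P(interim stops for talc) + P(interim does not stop, final rejects for talc). Both terms were computed exactly by enumerating every 2×2 table at the interim and carrying the continuing tables to the final size with binomial probabilities.

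At p = 45%, with 92 / 101 per arm and Fisher at both looks:

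- Final one-sided Fisher test alone: 3.41% / 3.84%.
- Adding a one-sided interim (which alone spends 2.90%): 5.10% / 5.55%, an increase of 1.69 / 1.71 points.
- Adding a two-sided interim (1.72% on the talc side): 4.28% / 4.73%, an increase of 0.87 / 0.89 points.

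Over null rates 35-65% in 1-point steps, final at one-sided 0.05:

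| Interim at 0.05 | Final | 50, then 92 or 101 per arm | 45, then 83 or 91 per arm |
|---|---|---|---|
| One-sided Fisher | One-sided Fisher | 4.97-5.71% | 5.3-5.9% |
| Two-sided Fisher | One-sided Fisher | 4.2-4.8% | 4.0-4.6% |
| One-sided Fisher | One-sided pooled z | 6.0-6.9% | 6.42-7.15% |
| Two-sided Fisher | One-sided pooled z | 5.3-6.0% | 5.15-6.02% |

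In the first row without dropout, error is at or below 5% at 5 of the 31 null rates (48-52%) with 92 per arm, and at none with 101. The z test alone already gives 4.5-5.3%, so part of the excess in the last two rows comes from that assumed test and not from the interim.

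If a stop favouring control is also counted as a false positive, a two-sided Fisher interim followed by a one-sided Fisher final gives 5.9-6.6% (50, then 92 or 101). A two-sided Fisher final would hold talc-favouring error at 2.8-4.3%, but it conflicts with the one-sided design.

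**Behaviour under 45% vs 65%.** The chance of stopping at the interim is 46% (two-sided) or 55% (one-sided) with 50 per arm, and 39% or 55% with 45. The mean observed difference at a stop is 27-30 points against a true 20.

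**The case against.** The strongest reply is that little is lost. A test for a difference is naturally read as two-sided. With Fisher, the only named test, and a one-sided final, talc-favouring error is then 4.2-4.8%, inside the design level. Even on the one-sided reading the worst case without dropout exceeds 5% by only 0.7 points. The higher figures need a z test that the text does not name. All of this stands as a statement about size.

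It does not show that the level is controlled. Where error stays below 5%, only Fisher's conservatism keeps it there. The same two-sided interim and one-sided final, in normal theory with correlation √(100/184) or √(100/202) between looks, give 6.2% or 6.3%.

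Three stronger readings are tempting, and the documents do not support them:

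- **A reader might infer inflation to about 8%.** Normal theory with one-sided 0.05 at both looks does give 7.9-8.0%, but the interim test is Fisher, which spends less than its nominal level.
- **A reader might infer that the rule cannot be repaired once interim data are seen.** If the trial continues, the final level can still be lowered. A final one-sided Fisher p<0.03 after a one-sided Fisher 0.05 interim has maximum error of 4.5% (50 then 92), 4.6% (50 then 101), 4.6% (45 then 83) and 4.9% (45 then 91) over null rates 5-95%.
- **A reader might take the overstated effect at a stop as evidence against this particular threshold.** Overstatement is common to early stopping, and a stricter boundary increases it.

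**Conclusion.** The concern holds as a defect of design with a modest effect on error. The plan orders termination on an unadjusted p<0.05 without sidedness or direction, divides no alpha and states no final level. Whether talc-favouring error ends just below or somewhat above 5% is therefore decided by choices the plan leaves open. A material loss of error control is not shown on every reading.

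The figures rest on equal arms, the assumed counts, null rates of 35-65% and a final test at the full one-sided 0.05. A reader might take that last item as the plan's stated rule; it is an inference from the power calculation. The wording gap itself depends on none of these assumptions.

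**What to change.** State the test, direction and sidedness at both looks. Replace the interim p<0.05 with a boundary that holds overall one-sided 0.05, preferably before interim data are seen. If the interim has already passed and the trial continues, lower the final level instead, and base the new level on the interim rule and the counts, not on the observed result.

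One example: stop only if talc is better with one-sided Fisher p<0.005, then test the final at one-sided Fisher p<0.045. Fisher's test does not exceed its nominal level, so total error is at most 0.005 + 0.045 = 0.05 for any arm sizes or null rate. The exact value is 3.2-3.7% at null rates 35-65% with 92 or 101 per arm. The boundary shape is the sponsor's choice.

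Say who decodes the arms for a directional rule, because the statistician is to be blinded to allocation.

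Cost in power under 45% vs 65%:

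| Per arm (interim, final) | Fisher 0.005 then 0.045 | Unadjusted one-sided Fisher, both looks | Loss (points) |
|---|---|---|---|
| 50, 101 | 85.4% | 87.9% | 2.5 |
| 50, 92 | 81.6% | 84.0% | 2.4 |
| 45, 91 | 80.9% | 84.2% | 3.3 |
| 45, 83 | 79.3% | 81.6% | 2.3 |

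All of these fall short of the stated 90%, but most of that gap is not due to the boundary: a single one-sided Fisher look has only 86.7% (101 per arm) or 82.2% (92).

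Early stopping under the planned effect falls from 39-55% to 18-24%. The mean observed difference at a stop rises from 27-30 to 33-35 points against a true 20, so the plan should also commit to reporting an estimate and interval adjusted for early stopping.
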